1. SUMMARY

Women breast cancer survivors are at increased risk for several negative health outcomes. Physical activity can reduce these risks, but activity levels in this population are low. Standard interventions that use self-regulation techniques (goal setting, self-monitoring, and feedback) are successful in the short term but do not produce the long-term activity maintenance needed for optimal health benefits. Their effectiveness might be improved by better connecting activity feedback to individuals' real-life experiences and values. Integrated regulation is a form of motivation related to personal values and identity and is strongly related to physical activity over time. Increasing this form of motivation could improve upon current intervention strategies, particularly in this population. Narrative visualization uses photographic, visual, and text annotation to tell a meaningful story with a data chart. This form of visualization can increase reflection, which in turn can predict integrated regulation and physical activity. We hypothesize that an intervention that encourages participants to create narrative visualizations from their step self-monitoring data will produce greater increases in physical activity than a self-regulation intervention. To test this hypothesis, we must first investigate the feasibility and acceptability of the narrative visualization intervention in a pilot randomized controlled trial. We will recruit 60 women breast cancer survivors (aged 55 – 79, < 150 minutes of physical activity per week) in two phases. In Phase I, 20 women will use prototype materials for one week and undergo cognitive interviewing to investigate feasibility and acceptability. Materials will be revised based on responses for use in the subsequent trial. In Phase II, we will randomize 40 participants to receive either the narrative visualization intervention or a standard self-regulation intervention for 12 weeks (with 12 weeks of no-intervention follow-up). Both groups will receive a wearable activity monitor and feedback app for use during the intervention period as well as an initial orientation/goal setting meeting and workbook. In the self-regulation group, participants will receive a workbook in which they will write and log their weekly goals. The narrative visualization group will also receive extended workbook content, a photo printer, and art supplies. The expanded workbooks will include spaces for posting daily photos and drawing explanations of step charts as well as reflection prompts relating the photos and charts to personal values and identity. Participants will be assessed at baseline, 12 weeks, and 24 weeks on changes to their activity, reflection, and integrated regulation. Feasibility indicators will include wear of the monitor and usage of the workbooks. Results from this study will be used to refine the intervention and to develop a follow-up study powered to investigate the relationships between reflection, motivation, and activity. Our overarching goal is to reduce the burden of cancer and improve quality of life among breast cancer survivors. This project represents a critical step towards this goal. Insights from the study will impact research and practice by testing a highly novel, scalable, and motivating intervention in a population at unique risk.

2. BACKGROUND AND RATIONALE

Breast cancer survivors are at risk for negative health outcomes related to both cancer and its treatment.^{1,2} Sustained habitual physical activity (PA) can reduce these risks,^{3,4} but PA levels are low in this population.^{5,6} Self-regulation interventions that use techniques such as goal setting, self-monitoring, and feedback can produce short-term PA increases⁷ but have rarely demonstrated long-term behavior change.⁸

A major limitation of self-regulation interventions is the lack of focus on motivation related to personal values and identity, which is called integrated regulation.⁹ Increasing evidence suggests that integrated regulation is strongly associated with PA over time.^{10,11} Individuals who self-monitor PA have reported that their adherence decreases over time because the feedback they are provided is inadequate: without an emotional connection to their values and everyday experiences, individuals are unsure of how to use and interpret reports of their step progress.^{12,13} Older breast cancer survivors in particular face issues related to the impact of treatment on their identities^{14,15} and desire their step goals and progress to be placed in the context of their broader values.¹⁶

Thus, a method for connecting step data to values, identity, and real-life experiences is needed. Reflection is the process of transforming experience into meaning.¹⁷ Brief experiments have found that self-monitoring alone did not produce reflection,¹⁸ and adding reflection prompts to self-regulatory PA programs increased PA.¹⁹ Using visuals to prompt reflection may be even more successful than written prompts.²⁰ Narrative visualization consists of using drawings, photographs, and text to annotate data charts to better tell a compelling personal story.^{21,22} This procedure could address limitations of current step self-regulation interventions and promote reflection and integrated regulation.

3. SPECIFIC AIMS AND OUTCOMES

3.1. SPECIFIC AIMS

Aim 1. Develop and refine reflection materials among a sample of sedentary breast cancer survivors.

Aim 2. Conduct a pilot randomized controlled trial comparing the self-monitoring + narrative visualization intervention to standard self-monitoring.

- **2a.** Determine the feasibility and acceptability of intervention procedures and materials.
- **2b.** Compare the effects of the interventions on objectively-assessed PA and psychological outcomes at 12 and 24 weeks.

3.2. Primary outcomes will be feasibility and acceptability. Specifically, indicators of feasibility and acceptability will include:

- **Attrition** per intervention condition as measured by study records
- **Adherence** to wear of the activity monitor as measured by daily step information in the Fitbit app
- **Adherence** to use of the workbook as measured by observation of photographs of each workbook page (number of photographs taken for values clarification activity, completion of written portion of values clarification activity, number of days with written entries, number of days with graphic entries, photos pasted into workbook, number of stickers pasted into workbook, number of additional drawings, number of “tag” annotations added to graphs, coded level of reflection of written entries)
- **Dose delivered** as measured by study logs of materials provision
- **Dose received** as measured by self-report
- **Adverse events** as measured by self-report and study records
- **Acceptability** will be measured using quantitative items in the 12 week and 24 week questionnaires as well as in the brief interview during the 12 week assessment

3.3. Secondary outcomes

- **Steps.** PA will be measured objectively using Actigraph wGT3X BT monitors. Wear time will be seven days at each assessment point. Because continuous measurement is not feasible, a week-long sample will be taken at the three assessment periods. Estimates will be valid if the monitor is worn ≥ 10 hours per day on ≥ 4 days. Non-wear time will be determined by 60 or more of consecutive minutes of zero activity counts. Because the emphasis of the intervention content is on walking, steps will be the primary measure of PA. We will also investigate minutes of moderate-vigorous intensity PA. Based on criteria used for the NHANES surveys, epoch length will be one minute, and activity counts over 2020 per minute will be considered moderate-vigorous intensity.²³
- **Anthropometric measurements** will include height (SECA stadiometer; baseline only), weight (Tanita research-grade scale), and waist circumference.
- **Additional psychological variables.** Table 1 shows the variables to be included in questionnaires at each time point.

Table 1. Measures

Variable	Measure	Sub-scales	Alpha	References
Motivation	Behavioral Regulation in Exercise Questionnaire-3	Intrinsic motivation, amotivation, and integrated, identified, introjected, and external regulation	0.73 to 0.86	24,25
Self-reflection	Self Reflection and Insight Scale	Engaging in self-reflection, need for self-reflection, insight	0.71 – 0.91	26
Engaged living	Engaged Living Scale	Valued living, life fulfillment	0.78 – 0.88	27
Values	Chronic Pain Values Inventory	Family, intimate relations, friends, work, health, growth	0.82	28
Basic psychological needs	Basic Psychological Needs in Exercise questionnaire	Autonomy, competence, relatedness	0.75 to 0.86	29
Exercise identity	Exercise Identity Scale	Exercise role identity, exercise beliefs	0.94	30
Body image	Body Image Scale	N/A	0.86+	31
Quality of life	Functional Assessment of Cancer Therapy – Breast	Physical, social, breast, functional ,emotional	0.90	32

4. STUDY DESIGN

This study will combine an initial formative, qualitative study with a pilot randomized controlled trial. The target population is breast cancer survivors aged 55 – 79 who are sedentary (< 150 minutes of physical activity per week), and who completed their primary cancer treatments at least 6 months prior to enrollment. This trial corresponds approximately to phases Ib (formative research to refine the intervention) and IIb (pilot randomized controlled trial to investigate feasibility and effect sizes) in the ORBIT model of behavioral intervention development. The trial itself will occur at a single center, but recruitment will occur at both UTMB and MD Anderson.

We anticipate that the duration of the Aim 1 phase will be approximately four months. From the beginning of recruitment to the final data collection point, we expect the trial to take one year to complete. The trial will consist of two arms: the narrative visualization intervention condition and an attention control intervention that includes only standard self-monitoring.

5. Study enrollment and withdrawal

5.1. Inclusion criteria for Aim 1

1. Age between 55 and 79
2. Female
3. Self-reported diagnosis of breast cancer
4. Participant is inactive (reports less than 150 minutes of moderate-vigorous intensity activity per week)
5. Able to read and understand English
6. Daily access to a smartphone or similar device compatible with Garmin or Fitbit app

5.2. Exclusion criteria for Aim 1

No exclusion criteria for the Aim 1 study will be used.

5.3. Inclusion criteria for RCT

1. Age between 55 and 79
2. Female
3. Self-reported diagnosis of breast cancer
4. BMI is between 18 kg/m² and 40 kg/m²
5. Willingness to be randomized to any condition
6. Participant is able to walk for exercise
7. Able to read and understand English
8. Daily access to a smartphone or similar device compatible with Fitbit app
9. PAR-Q+ indicates that physical activity would be safe (with note from physician required if any heart-related questions are endorsed)

During the COVID-19 pandemic, the following inclusion criteria will be implemented

10. Must have access to teleconference capability from home (i.e. Skype, FaceTime, Zoom or other teleconference programs with smart phone or webcam technology).

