5.5. Rationale for inclusion/exclusion criteria

We will not recruit individuals who cannot speak English due to the need to understand the app, which is in English.

Participants will likely be moderate risk as designated by the American College of Sports Medicine, and thus we want to be conservative in our eligibility criteria. If participants endorse any question on the PAR-Q+, they will automatically be ineligible due to unacceptably high risk unless they produce a note from their physician clearing them for participation.

We will focus specifically on cancer survivors who are at least six months post major treatment to ensure that complications do not impact the safety of exercises.

Other exclusion criteria exist to exclude variables that could potentially affect participation in the trial. We will also exclude those with a BMI indicating that they are underweight as we are interested in adults of normal weight, overweight, and obese status. Underweight may indicate other health problems that could compromise participant safety. We will include obese adults up to a BMI of 40, but those over 40 are likely to be substantially different from our target population and will require independent study in the future.

Other health exclusions are for the purposes of safety and unbiased data (e.g., substance use disorder).

No exclusion criteria or quotas will be related to race, ethnicity, or gender.

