5.6. Recruitment strategies

Participants will be recruited using several methods:

1. In-person recruitment at UTMB and MD Anderson clinics
2. Phone and email screening of eligible patients at MD Anderson clinics
3. Referrals from practitioners at both institutions
4. Flyers and brochures available in treatment and waiting areas of both institutions, community clinics in Galveston and surrounding areas.
5. Mailed letters and emails to members of research and cancer registries at both institutions
6. Targeted Facebook advertisements
7. Emails to local organization listservs (each institution, local cancer support groups, etc.)
8. Presentations at local cancer and wellness events
9. As necessary, newspaper and radio advertisement

Specifically, recruitment of MD Anderson patients may occur by flyer, in-person, by email, or by phone. Study staff at MD Anderson will review upcoming patient appointments in the clinic via EPIC. Participants who look to be eligible will be called over the phone to explain to them the study procedures and see if they are interested in participating. This procedure is regularly used successfully by our collaborators at MD Anderson. Whereas at UTMB we must obtain practitioner permission to approach patients, all MD Anderson patients have provided consent to be approached by research-related phone calls. Reciprocal approval of all screening materials, protocols, etc by the MD Anderson IRB will be obtained prior to any recruitment. Participants will also be screened at that time to ensure that they are eligible to participate in the study. If the patient is interested and eligible, UTMB study staff will call to set up an appointment for informed consent, baseline assessment, and randomization/study orientation. MD Anderson staff will assist with this pre-screening but will not be involved in intervention or assessment procedures. MD Anderson clinics will be a recruitment site only, not an intervention site (i.e., UTMB consent forms will be used, MD Anderson personnel will not have access to any non-screening-related study data, etc.).

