8.1. Screening

We have collaborated with oncologists at various clinics to expand our effort in recruitment. A HIPAA waiver request form has been completed. With the oncologist's approval, we will pre-screen patients via medical records for eligibility. The oncologists will refer their patients. We will not approach UTMB patients unless we have oncologist's and patient's permission.

For patients at MD Anderson clinics, as discussed above in section x, staff will review upcoming patient appointments in the clinic via EPIC and call potentially eligible participants. Whereas at UTMB we must obtain practitioner permission to approach patients, all MD Anderson patients have provided consent to be approached by research-related phone calls and emails. If the patient is interested and eligible, UTMB study staff will later call to set up an appointment for informed consent, baseline assessment, and randomization/study orientation.

Research staff will use the RCT screening guide, either in person or by phone, to determine eligibility in the study. Should the participant be found eligible, the staff member will schedule an appointment for informed consent and enrollment.

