- Provide gift card and document

COVID-19 adjustments for consenting/enrollment:

- We will collect the activity monitor and questionnaires during a brief in-person visit. Study staff will wear personal protective equipment and sanitize equipment as needed. The gift card will be provided at the conclusion of this visit.
- While reviewing data in January of 2021, we noticed that many follow-up assessments scheduled after March of 2020 were missing. We suspect many of these missing visits were due to COVID-19 in some form and wish to investigate and gather as much information as possible from these participants. Thus, we are amending our procedures for follow-up to include the possibility of contacting participants more than one month after their indicated follow-up time. These visits will be amended to consist only of questionnaire, interview, and if possible collection/photography of materials. We have added several questions about COVID-19 to our interview guide to find out more about whether or not participants used intervention materials during the pandemic. The consent form has been updated to include these procedures. When we contact participants with no follow-up data, we will conduct a new consent interview and re-consent them using the new form to ensure that they are fully aware of the updated procedures.

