11.5. Protection against risks

General. Inclusion/exclusion criteria will allow us to exclude from the study anyone who is potentially at higher risk for developing complications due to research procedures. Participants will be able to withdraw from the study at any time if study procedures are upsetting or painful for them. We will closely monitor all participants for adverse events (see data safety and monitoring plan below).

Confidentiality. All data collected will be confidential. The risk of breached confidentiality of potentially sensitive data is minimal and comparable to the risk inherent in any human subjects research project. We will take standard precautions to ensure that personal health information is not identifiable, including:

- Paper copies of questionnaires and screening forms will be kept in a locked file cabinet in the research coordinator's locked office. ID numbers will be used on these forms to match them to individual participants. The database matching ID numbers to identifying information will be individually password-protected and kept separately on the password-protected server. We will abstract wear and step data from their Fitbit app accounts weekly into a database kept on this server, but we will not otherwise collect data from the app.
- Data collected on measurement equipment will be uploaded to the server as soon as possible after collection. Then, it will be erased from the equipment. ID numbers will be used for participant identification on all physiologic measurement equipment as an added layer of protection. No identifying data will be kept on measurement equipment or on portable data storage devices such as laptops or USB drives.
- Transcripts and scans of workbook pages will be saved by ID number, with any identifying information redacted. These files will be kept on a password-protected server.

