Injury, pain, fatigue. Exercise may produce minor injuries or, much less likely, adverse cardiac events. Though starting an exercise program can be minimally to moderately risky, depending on the individual, when participants are properly screened the benefits outweigh the risks. Exercise can improve fitness, quality of life, cardiometabolic indicators of health, mood, fatigue, and a number of other outcomes (see research plan for references). The goals that we will suggest will increase slowly to ensure safety. [name] is a physician. She will review all adverse events and data abstracted from the apps that indicate potentially dangerous activities.

Psychological stress. Participants may refuse to answer any of the questions, take a break, or stop their participation.

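### Sections 5.3 and 5.5 give different PAR-Q+ triggers for the physician's note, so a woman with only a non-heart endorsement and no note can be read as eligible under one and is ineligible under the other

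*Combined protocol and SAP*

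**What the plan says.** Section 5.3, item 9, makes it an inclusion criterion for the RCT that the PAR-Q+ shows physical activity to be safe. A parenthesis adds a condition: "with note from physician required if any heart-related questions are endorsed". The item does not say what happens when a woman endorses a question that is not heart-related.

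Section 5.5, the rationale for the criteria, states: "If participants endorse any question on the PAR-Q+, they will automatically be ineligible due to unacceptably high risk unless they produce a note" from a physician clearing her. The trigger here is any question. The same paragraph gives the motive: "we want to be conservative in our eligibility criteria".

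On who screens, section 5.6 says of the telephone contact with MD Anderson patients: "Participants will also be screened at that time to ensure that they are eligible to participate in the study". It describes the MD Anderson staff as assisting with pre-screening. Section 8.1 says: "Research staff will use the RCT screening guide, either in person or by phone, to determine eligibility in the study". Neither section says at which contact the PAR-Q+ is given.

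**The concern.** The numbered criterion and its rationale attach the physician's note to different sets of answers. A screener working from the list in 5.3 would look for a note only when a heart-related item is endorsed. A screener working from 5.5 would turn away anyone with any endorsement and no note.

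What is at stake is consistent safety screening. The protocol rests its protection of participants on these criteria. Section 11.5 (Protection against risks) says: "Inclusion/exclusion criteria will allow us to exclude from the study anyone who is potentially at higher risk". The same section makes its risk-benefit statement conditional: "when participants are properly screened the benefits outweigh the risks". Section 5.5 describes the women it would turn away as carrying an unacceptable risk. If the entry rule can be read in two ways, proper screening has no single meaning, and staff at two institutions take part in it.

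**Working it through.** No arithmetic applies to the core point. The check sets the two rules side by side and then looks for any text that reconciles them.

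**Inputs**
- Section 5.3, item 9: the PAR-Q+ must indicate safety; a note is required for heart-related endorsements.
- Section 5.5: any endorsement means ineligible unless a physician's note clears the participant.

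**Case by case**

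| PAR-Q+ answers | Note | Section 5.3, item 9 | Section 5.5 |
|---|---|---|---|
| None endorsed | not needed | passes | passes |
| Heart-related item | no | fails | fails |
| Heart-related item | yes, clearing | can pass | can pass |
| Non-heart item only | yes, clearing | can pass | can pass |
| Non-heart item only | no | no note required; can be read as eligible | automatically ineligible |

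Only the last row diverges. In the fourth row, 5.3 does not say outright that a note settles a non-heart item, but both texts allow her to enter.

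**Search for a reconciling passage**
- The PAR-Q+ is named twice in the document, once in 5.3 and once in 5.5.
- Exclusion 9 in section 5.4 is a discretionary clinical judgment and mentions neither the PAR-Q+ nor a note.
- The visit steps in 8.2 and 8.3 mention neither.
- Section 9.1 has the Principal Investigator review screening results, which presupposes a settled definition of ineligibility.
- Weekly review of activity data (11.4) and physician review of adverse events and app data (11.5, Protection against risks) act after entry and do not define the entry rule.
- The RCT screening guide named in 8.1 is not supplied.

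**Size**
- Number affected = number screened × proportion endorsing only non-heart items × proportion of those without a note. None of the three terms is given, so no figure can be computed.
- Forms to review: 40 planned RCT participants (section 1) × 1 screening form = about 40. This is a planning figure. Consent (8.2) comes before randomization (8.3), so the number of women who consented could be somewhat higher.
- Timing: section 8.5 records that in January 2021 the team found "many follow-up assessments scheduled after March of 2020 were missing". Enrolment had therefore begun before this text was written.

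**The case against.** The strongest reply is that 5.3 is silent on the disputed case and does not oppose 5.5. The main clause of item 9 requires the PAR-Q+ to indicate safety, and any endorsement could be taken to mean that it does not. On that reading 5.5 completes 5.3, and staff can comply with both by following the wider rule. This reading is possible and fits the stated wish to be conservative. It does not settle the matter. If every endorsement already called for a note, limiting the parenthesis to heart-related questions would serve no purpose, and 5.5 does not say that it adds to item 9.

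The second reply is that the screening guide decides practice, and that controls surround it. Screening materials go to the UTMB IRB (11.1), and MD Anderson's IRB must approve them before recruitment there (5.6). Several other criteria in 5.3 and 5.4 also screen for non-heart risks, such as recent major treatment, stroke, joint replacement and orthopedic problems. This stands as a limit on the likely harm, and nothing shows that the teams applied different rules. But none of these provisions states the PAR-Q+ trigger, and a guide that contains one rule would still leave the two protocol sections worded differently.

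A third reply concerns the look-back. It might seem to adopt the 5.5 trigger as the standard, and its safety yield may be small because many women had probably finished the 12-week intervention by early 2021. The second part is fair. On the first, the look-back only identifies the cases on which the two texts disagree; it does not judge them.

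**Conclusion.** The concern holds. The difference in wording is certain, and it sits in a safety criterion on which the protocol's own risk statement depends. It can change the eligibility decision in one case: a non-heart endorsement alone, without a note. That conclusion assumes only that item 9 can be read as its parenthesis is written.

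Whether any enrolment decision was affected is unknown, because the screening guide is not supplied and no screening counts or endorsement rates are given. No between-arm bias, analysis error or sample-size consequence follows. The point should be fixed, but it does not threaten the trial's conclusions.

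**What to change.** Reconcile section 5.3, item 9, with section 5.5 so that both state the same PAR-Q+ clearance rule, and carry that rule into the RCT screening guide. The choice of rule belongs to the investigators and the study physician. Whichever they choose, the text should say explicitly how a woman who endorses only a non-heart item is handled, with and without a note, and at which contact the PAR-Q+ is given.

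As a safety check, review the existing RCT screening forms for enrolled women who endorsed only a non-heart item and had no note, and refer any found to the study physician. Do not class these automatically as deviations. Section 12.4 defines a deviation as noncompliance with the protocol, and an enrolment consistent with the text in force at the time need not be one.

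Cost: a short amendment, an update of the guide if it differs, and review of about 40 forms. The only downside is staff time.
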